#### Comparison methods

The primary outcome is a binomial outcome measured as a surgical complication and/or requirement for reoperation for complication management  $\leq 6$  months after initial PFDD or PFD. To account for within cluster correlation, possibly variable cluster size and the relatively small number of clusters in this cluster randomized trial, generalized estimating equations (GEE) with small-sample correction or random effect logistic regression will be used for the primary analysis of this cluster randomized trial [35, 36].

Secondary outcomes include Treatment Efficacy variables and Quality of Life variables. Continuous variables measured at 3 time points over the 12 (+/- 2 months) month follow-up will be analyzed using longitudinal analysis with linear mixed models including the random cluster effect. Binomial and ordinal data will be analyzed using GEE methods accounting for cluster. In the case where the patient returned outside the planned study follow-up window, a secondary analysis will include those visits up to 24 months.

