The non-inferiority margins for this trial were determined in conjunction with a panel of experts on CM+SM and related treatment (the Park-Reeves investigators), our non-physician stakeholder partners, and our patient partners, [name], [name], [name], [name], [name], [name], and [name]. Using a clinical, Delphi-type approach [46] for the complex measure of clinical improvement, the research team agreed upon a non-inferiority margin of no more than 20% lower response for PFD from the PFDD group. The clinical improvement rate (the improvement from baseline to 12 months) for the PFDD group was provided as 78.6% in the Durham study [27]. Thus, with the sample size of 72 subjects per group (after an assumed 2% dropout), we can conclude the non-inferiority of the PFD to PFDD with a margin of 0.17 units (α =0.05, 80% power). This corresponds to clinical improvement rate of 61.6% in the PFD group. It was shown in the Durham study that the clinical improvement following PFD was 64.6%.

Determine if PFD provides non-inferior clinical improvement compared to PFDD (Non-inferiority Design)							
Outcome	PFDD	PFD	Data Source	Non-inferiority Margin	α-level	Subjects per group	Power
Clinical Improvement	44/56 (78.6%)	51/79 (64.6%)	Durham [27]	0.17	0.05	72	80%

For these calculations, the drop-out rate is assumed to be 2%, and the one-sided type I error rate is 0.05.

After determination with the Delphi method, the non-inferiority margin was subsequently confirmed as appropriate using Rothman's 95-95 approach [47, 48] and the FDA guidelines for selecting the non-inferiority margin for non-inferiority clinical trials [49]. Using these methods, the non-inferiority margin was estimated using the effect of the standard treatment (PFDD) from Durham's meta-analysis [27], with the lower 1-sided 95% confidence interval for the random-effects meta-analysis calculated to be used as a non-inferiority margin. When the data from the PFDD group from the Durham study was used for the clinical improvement outcome, the 95% lower 1-sided confidence interval from the random effects model was calculated as 0.611. In our proposal, we defined the non-inferiority margin as the difference between the clinical improvement rates in the PFDD and PFD groups ($\pi_{PFDD} - \pi_{PFD}$). For the clinical improvement outcome, this corresponds to the non-inferiority margin of 0.786 – 0.611 = 0.175 units. Therefore, our

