recommended non-inferiority margin of 0.175 units for the clinical improvement outcome is consistent with the FDA-recommended largest acceptable non-inferiority margin of 0.175 units.

In contrast to clinical improvement, syrinx regression is an objectively measurable and easily quantifiable outcome. It is measured by comparing syrinx size on MRI scans obtained before and after surgery. When the effective sample size is 68 subjects per group, and assuming 89.1% syrinx regression rate in the PFDD group [27], the non-inferiority margin is 0.135 units to reach 81% power. A non-inferiority margin of 0.135 units represents no more than 13.5% reduction from the PFDD group in terms of syrinx regression. Note that a one-sided type I error rate of 0.05 was assumed, and the 'Two group test of equivalence in proportions' option in nQuery Advisor was used for the sample size calculations.

Determine if PFD provides non-inferior syrinx regression compared to PFDD (Non-inferiority Design)							
Outcome	PFDD	PFD	Data Source	Non-inferiority Margin	α-level	Subjects per group	Power
Syrinx Regression	261/293 (89.1%)	31/38 (81.2%)	Durham [27] and PRSRC	0.135	0.05	72	81%

For these calculations, the drop-out rate is assumed to be 2%, intra-class correlation coefficient is 0.05, and the onesided type I error rate is 0.05.

Aim 3: Power Calculations

Based on preliminary data using the Chiari Health Index in Pediatrics (CHIP)[50], we observed a 0.12±0.16 unit improvement in Quality of Life (QOL) scores following PFDD. Our sample size of 72/group (effective sample size of 68/group) will provide 82% power to detect a 0.20±0.16 unit improvement in CHIP QOL scores following PFD (α =0.05). Both from an analytical standpoint and from the view of PRSRC investigators and our patient partners, this value represents both a significant and meaningful increase in QOL

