The primary outcome is a binomial outcome measured as a surgical complication and/or requirement for reoperation for complication management ≤ 12 (+/- 2 months) months after initial PFDD or PFD. To account for within cluster correlation, possibly variable cluster size and the relatively small number of clusters in this cluster randomized trial, generalized estimating equations (GEE) with small-sample correction or random effect logistic regression will be used for the primary analysis of this cluster randomized trial [35, 36].

Specifically, a GEE model with a logit link function and adjustment for baseline covariates can be expressed as follows:

$logit(\pi_{ij}) = \mu + \delta T_i + x_{ij}\beta$

where $T_i = I$ if group *i* is assigned PFD and 0 otherwise. Accordingly, δ is the intervention effect. Let x_{ij} is the p-dimensional vector of group-level of individual level covariates from individual *j* (*j* = 1, ..., n_i) nested in center *i* (*i* = 1, ..., # of active centers here); and β is the vector of covariate effects. Also let the outcomes (CSF-related complication ≤ 6 months, yes/no) are independently distributed as $y_{ij} \sim \text{Bernoulli}(\pi_{ij})$. Further let, μ be the log-odds of positive outcome ($y_{ij} = 1$) for PFDD subjects with reference values for covariates ($x_{ij} = 0$) and average random effect ($\gamma_i = 0$). The exchangeable correlation structure will be used for the within-group homogeneity for the correlation structure of the outcomes. Note that, this correlation parameter corresponds to the intraclass correlation coefficient (ICC).

Specific Aim 2:

Hypothesis: Clinical improvement and syrinx regression provided by PFD will be non-inferior compared to those provided by PFDD.

Anticipated Outcome: Clinical symptoms, neurological function, and syrinx regression ≤ 12 months (± 2 months) provided by PFD will be non-inferior compared to those provided by PFDD. The non-inferiority margin is defined as the difference between the outcome rates by treatment. For the clinical improvement outcome, a non-inferiority margin of 0.17 units will be used. A non-inferiority margin of 0.135 units will be used for the syrinx regression outcome.

Clinical symptoms, neurological function, and syrinx regression are defined as rates of change from baseline to 12 months. The 1-sided confidence interval for the difference in rates between the PFD and PFDD groups will be calculated and compared to the corresponding non-inferiority margins.

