Second Chiari surgeries will be analyzed as 1) the proportion requiring a surgical revision and 2) the type of second surgery performed (same or cross-over). The 1-sided confidence interval for the difference in rates between the PFD and PFDD groups will be calculated and compared to the corresponding non-inferiority margins.

Specific Aim 3:

Hypothesis: With fewer surgical complications, PFD will be associated with superior QOL compared with PFDD.

Anticipated Outcome: PFD will have superior QOL and will show improvements in overall QOL over time (≤ 12 months post-operatively (± 2 months)) compared to PFDD. In particular, both physical metrics (evaluated by pain frequency, pain severity and non-pain symptoms) and psychosocial metrics will improve at a higher rate and in a shorter period of time after PFD compared to PFDD.

Secondary outcomes include Treatment Efficacy variables and Quality of Life variables. Continuous variables measured at 3 time points over the 12-month follow-up will be analyzed using longitudinal analysis with linear mixed models including the random cluster effect. Binomial and ordinal data will be analyzed using Mixed Model methods accounting for cluster. In addition, sensitivity analyses will be conducted where the missing data points will be imputed based on the last observation carried forward.

It should be noted that for Aim 3, primary analyses will be based on the QoL exam performed at 10 to 14-month window. A sensitivity analyses will also be performed based on the last QoL exam available at any time \geq 3 months after surgery. Analyses based on the mixed effect model will also be performed where both cluster effect and error terms will be random.

Missing data: Based on PRSRC data and early data from this trial, loss to follow-up rate is expected to be low (<2%). To prevent missing data, we will meet with patients at 1 month, 3-6 months and at 12+/-2 months after the procedure. Every effort, including phone call reminders to patients, will be made to decrease loss to follow-up. Loss to follow-up, missing data, and the reasons leading to loss of follow-up or data will be recorded. In case of missing data, we will impute missing data using different methods. Because of the repeated measures nature of the data, the 'last observation

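### The 80% power for Aim 2 clinical improvement carries no design effect, and the interval that decides non-inferiority is not tied to any of the plan's cluster-adjusted methods

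*SAP*

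**What the plan says.** **Decision rule.** SAP 7.5, Specific Aim 2, gives margins in rate units (0.17 for clinical improvement, 0.135 for syrinx regression) and then states: "The 1-sided confidence interval for the difference in rates between the PFD and PFDD groups will be calculated" and set against the matching margin. The sentence is repeated for second Chiari surgeries. It names no model, standard error, degrees of freedom or centre term.

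**General rule for secondary outcomes.** Further on in SAP 7.5, under Specific Aim 3: "Secondary outcomes include Treatment Efficacy variables and Quality of Life variables", followed by "Binomial and ordinal data will be analyzed using Mixed Model methods accounting for cluster". No link function is given. The corresponding Protocol text (9.5, Comparison methods) reads: "Binomial and ordinal data will be analyzed using GEE methods accounting for cluster". SAP 7.5 also plans, under Final Comparative Analysis, to weight clusters equally and refers to cluster-level summary scores. SAP 7.2.1 treats centres as the unit of inference.

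**Power.** SAP 7.2.1 bases clinical improvement on 72 per group: "with the sample size of 72 subjects per group (after an assumed 2% dropout"). The footnote to that table lists dropout and alpha but no intraclass correlation (ICC). The next calculation, for syrinx regression, starts: "When the effective sample size is 68 subjects per group". Aim 3 (CHIP) likewise reduces 72 to an effective 68.

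**The concern.** Clinical improvement and syrinx regression are the two outcomes that SAP 1.2 makes primary for Aim 2. One is powered with an allowance for clustering and the other without, so the two stated powers (80% and 81%) are not on the same footing.

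The interval matters more in principle. For Aim 1 the SAP spells out the model, link, correlation structure and small-sample correction. For Aim 2 it gives only the form of the result. In a non-inferiority test, an interval that is too narrow favours the hypothesis, so a missed cluster adjustment raises the chance of a false claim. Leaving the method open also allows it to be chosen after the data are seen. There is a scale problem too. The only link function that the SAP states is the logit, for Aim 1, and a logit model does not by itself give a limit that can be compared with a margin in rate units.

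**Working it through.** **Inputs.** All are from SAP 7.2.1.
- Clinical improvement: PFDD rate 0.786 ("for the PFDD group was provided as 78.6" per cent), PFD taken as equal for power, margin 0.17, one-sided alpha 0.05, 72 per group.
- Syrinx regression: rate 0.891, margin 0.135, effective 68 per group; its footnote gives ICC 0.05.
- Design effect: DE = 1 + (m − 1) × ICC, with m = 6 and ICC = 0.01. For variable cluster size, DE' = 1 + {(cv² + 1)m − 1} × ICC, with cv = 1.08 and m = 2.9.

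**Formula.** SE = √[2p(1 − p)/n]; power = Φ(margin/SE − 1.645).

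**Step 1: reproduce the stated 80%.** SE = √(2 × 0.786 × 0.214 / 72) = 0.0684. Then 0.17/0.0684 = 2.487, and Φ(2.487 − 1.645) = 80.0%. The stated figure is matched with independent patients and no design effect.

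**Step 2: the syrinx calculation as a check.** At n = 68 the power is 81.1%, against 81% stated. At n = 72 it would be 83.0%. So this calculation does use the reduced number.

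**Step 3: where 68 comes from.** It is not dropout, because that is already removed: 148 × 0.98 = 145, or 72 per group. The SAP does not show the step, but 72/68 = 1.06, which is the DE' that the SAP reports for m = 2.9, cv = 1.08 and ICC = 0.01. The footnote's ICC of 0.05 would give DE = 1 + 5 × 0.05 = 1.25 and 72/1.25 = 57.6, so it does not match the 68.

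**Step 4: clinical improvement with clustering.** Effective n = 72/DE. The last column is 1 − Φ(1.645/√DE), the true one-sided error at the margin if the interval treated patients as independent.

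| Case | DE | Effective n | Power | Error if unadjusted |
|---|---|---|---|---|
| Observed ICC 0.000059, m = 6 | 1.0003 | 72.0 | 80.0% | 5.0% |
| ICC 0.01, m = 6 (SAP) | 1.05 | 68.6 | 78.3% | 5.4% |
| Effective n used for syrinx and CHIP | 1.06 | 68 | 78.0% | 5.5% |
| ICC 0.01, cv 1.08 with m = 6 (my pairing) | 1.12 | 64.3 | 76.0% | 6.0% |
| ICC 0.05 (syrinx footnote), m = 6 | 1.25 | 57.6 | 71.9% | 7.1% |

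At DE 1.05, 80% power would need 72 × 1.05 = 75.6, so 76 analysed per group.

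**Step 5: can the interval be derived from the named methods?**
- Cluster-level summaries (SAP 7.5): could give a rate difference, but are not cited for the Aim 2 interval.
- Mixed model (SAP 7.5): accounts for cluster, but no link is stated. With a logit link it gives an odds ratio conditional on centre.
- GEE (Protocol 9.5): accounts for cluster, and again no link is stated for secondary outcomes. With a logit link it gives a marginal odds ratio.

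Each could be made to yield the limit. None is named as its source, and the two documents differ on the model.

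**The case against.** A reader might infer that the Aim 2 decision rests on an ordinary two-sample interval, or that a mixed model is the only cluster-adjusted method on offer. The documents support neither. The interval sentence is silent on variance, not explicit about independence. Around it stand centres as the unit of inference, equal cluster weights and cluster-level summaries, mixed models accounting for cluster that expressly cover efficacy variables, and GEE in the Protocol. The intent to adjust is clear.

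The scale problem is also not certain. SAP 1.2 averages the binary symptom scores into one overall score per patient, and a linear mixed model with a random centre effect could give a difference on that scale directly. That is a possible route, but the SAP does not state it. The power calculation treats improvement as a simple proportion.

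On size, a reader could stack ICC 0.05, cv 1.08 and m = 6 to reach DE' 1.60, with power 62.6% and error 9.7%. No document combines those values: the SAP pairs that cv with m = 2.9, and the recalculation replaced ICC 0.05 with 0.01. At the ICC actually observed, the effect vanishes. However, that ICC came from 47 patients in the Aim 1 recalculation, and the SAP expects it to change. No ICC is given for improvement or syrinx regression.

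Finally, SAP 7.2.1 in one place gives the clinical-improvement margin as 0.175, and at 68 per group that margin also yields 80%. So 80% is not unreachable with a design effect. But the stated calculation uses 72 and 0.17, and 0.17 is the margin that SAP 7.5 applies.

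What stands: the interval is not linked to a method, the documents name different models, and the design effect is missing from one of the two Aim 2 power figures.

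**Conclusion.** The point holds in two parts, both modest in size.

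1. The stated 80% power for clinical improvement is an independent-patients figure. On the basis used for syrinx regression and CHIP it is 78.0% (78.3% at DE 1.05). It falls to 76.0% if cv 1.08 applies at m = 6, and to 71.9% at ICC 0.05. The last two are sensitivity cases.
2. The SAP does not say how the one-sided limit that decides non-inferiority allows for centre. This is a gap in specification; it does not show that clustering will be ignored. If it were ignored, the one-sided error would be about 5.4% at DE 1.05, or 6.0% and 7.1% in the sensitivity cases, against 5%.

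These figures assume equal true rates of 0.786, a normal approximation with unpooled variance, and a design effect for improvement like the one the SAP derives for complications.

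**What to change.** - In SAP 7.2.1, restate clinical-improvement power at the effective sample size (about 78% at 68 per group), and correct either the ICC of 0.05 in the syrinx footnote or the 68 so that they agree. Give the clinical-improvement margin as one value throughout.
- In SAP 7.5, Specific Aim 2, state that each rate difference and its one-sided limit come from one named method on the rate-difference scale that allows for centre, with a small-sample correction, and that this limit is the one compared with the margin. An identity-link GEE, standardised marginal predictions with a cluster-robust standard error, or an analysis of cluster-level summaries would each serve. The choice matters less than fixing it before the data are analysed.
- Reconcile the Protocol's GEE with the SAP's mixed model for binary secondary outcomes.

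The cost is wording only, with no new data. The intervals may be slightly wider than unadjusted ones, and the stated power drops by about 2 points.

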complications are remarkably consistent with those reported in the meta-analysis by Durham and Fjeld-Olenec in 2008 (Table 2)[27], with complications noted in 17.8% following PFDD versus 2.7% after PFD. In addition, a corrective neurosurgical procedure for complication management was needed more often after PFDD compared to PFD (10.1% versus 2.7%). However, repeat decompression surgery for persistent disease was required in only 5.0% of PFDD cases versus 12.3% after PFD.

In planning a clinical trial for CM+SM, it is important to select appropriate inclusion criteria for study patients in order to: 1) enhance homogeneity in disease severity among study participants; 2) permit appropriate comparisons across participants and groups; and 3) ensure clinical equipoise among treating physicians. With this goal in mind, our group recently created the Chiari Severity Index, or CSI, a pre-operative instrument that stratifies children with CM+/-SM based on their probability of postoperative improvement[12]. The CSI was developed in conjunction with patient and families and uses their input as a critical arbiter of outcome. Two advanced methodologies, sequential sequestration and conjunctive consolidation, were used to identify key clinical and radiographic predictors of clinical outcome and then to integrate them into one useful CSI (Fig. 3).

We also recently completed a systematic review of outcome methods used in studies of CM+SM and noted that studies of CM+SM were significantly impeded by inconsistent and limited methods evaluating clinical of outcomes[28]. The majority of papers used a clinician's "gestalt" impression of symptomatic improvement (Fig. 4). Only 3 papers used scales validated in patients with CM+/-SM, and only 7 articles incorporated patient-response instruments. Our review emphasized the need for CM+SM-specific patient-based instruments to improve research in this field [28].

**Figure 3**. The Chiari Severity Index, or CSI, was developed using sequential sequestration of pre-operative clinical and radiographic parameters, followed by conjunctive consolidation of independent clinical and radiographic indices via [12]. Syrinx size was the only radiographic measure associated with clinical outcome, with a critical threshold of 6 mm diameter.

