1.2 Secondary Objectives

Specific Aim 2: Determine if PFD provides non-inferior clinical improvement and syrinx regression compared to PFDD.

Hypothesis: Clinical improvement and syrinx regression provided by PFD will be non-inferior compared to those provided by PFDD.

Anticipated Outcome: Clinical symptoms, neurological function, and syrinx regression ≤ 12 months will be non-inferior following PFD when compared with PFDD.

- Rates of revision decompression surgery (PFD or PFDD) and progression of spinal deformity ≤12 months after PFD also will be non-inferior to PFDD. Please note that the time window is ≤12 months. When there are multiple visits within this window, the visit with the closest to 12 months after surgery will be used.
- For this aim, clinical symptoms and syrinx regression ≤12 months will be used as the primary outcome variable. Results based on the rates of revision decompression surgery and progression of spinal deformity will be exploratory.

Corresponding Variable Names for 'Clinical Improvement'

• Outcome – Scores, Limonadi/Binary -> compare for symptoms and neurological deficits

- Timeframe compare preoperative to:
- ≤ 6 weeks
- 3-6 months
- 12 (+/- 2) months (primary)
- Binary Scoring is primary
- Limonadi Scoring specifics:
- Each subject was given a score for each symptom at each visit, 2=resolved, 1=improved, 0=stable, -1 = worse.
- Symptom scores within a patient were then averaged across visits (per Limonadi paper) to get patient-level symptom-specific scores.
- These patient-level symptom-specific scores were then averaged to get a single overall score per patient.
- These single overall scores per patient were then averaged within site randomization to get group comparisons between sites randomized to PFD and sites randomized to PFDD.
- Binary Scoring specifics:
- Each subject was given a binary score for each symptom at each visit, 1=positive outcome, 0=negative outcome.
- Symptom scores within a patient were then averaged across visits (per Limonadi paper) to get patient-level symptom-specific scores.
- These patient-level symptom-specific scores were then averaged to get a single overall score per patient.
- These single overall scores per patient were then averaged within site randomization to get group comparisons between sites randomized to PFD and sites randomized to PFDD.

Symptoms						
	Double Vision					
	Sensory Symptoms					
	Weakness Symptoms					
	Dysphagia					
	Hoarseness					
	Choking					

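### SAP 7.5 compares second Chiari surgeries with non-inferiority margins that neither document defines

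*SAP*

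**What the plan says.** SAP 7.5, under Specific Aim 2, sets two margins: "For the clinical improvement outcome, a non-inferiority margin of 0.17 units will be used" and "A non-inferiority margin of 0.135 units will be used for the syrinx regression outcome". It then turns to repeat operations: "Second Chiari surgeries will be analyzed as 1) the proportion requiring a surgical revision", and secondly by whether the repeat operation was the same procedure or the other one. The rule for these is: "The 1-sided confidence interval for the difference in rates between the PFD and PFDD groups will be calculated and compared to the corresponding non-inferiority margins". The same sentence closes the preceding paragraph, where "compared to the corresponding non-inferiority margins" refers to the two margins just named.

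SAP 1.2 and the Protocol (Objectives, 1.2, 3 and 9.1) all expect PFD to be non-inferior on revision and on progression of spinal deformity. SAP 1.2 adds: "Results based on the rates of revision decompression surgery and progression of spinal deformity will be exploratory". On prior data, Protocol 7.2.1 reports that "repeat decompression surgery for persistent disease was required in only 5.0% of PFDD cases versus 12.3% after PFD".

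**The concern.** A non-inferiority rule needs a threshold, and for second surgeries the SAP refers to one that is not there. The two existing margins do not carry over. SAP 7.2 defines the margin as the PFDD rate minus the PFD rate for an outcome where higher is better. For revision, higher is worse, so the sign must be reversed, and the prior PFDD rate is about 5% or less rather than 80% to 90%. The type of second surgery has no better or worse direction, so non-inferiority has no meaning for it.

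The outcome matters to the comparison. Protocol 2.2 raises a higher need for revision as a possible drawback of PFD, and the prior data in both sources point that way. The primary outcome counts reoperation only when it manages a complication, so repeat decompression for persistent disease falls outside it. A statement that PFD is non-inferior on revision would carry weight with families and surgeons, and the plan gives no basis for making or refusing it.

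**Working it through.** **1. Reproduce the plan's own Aim 2 figures (SAP 7.2).**
- Clinical improvement: 78.6% in both arms, margin 0.17, one-sided alpha 0.05, 80% power. n = 2 × 0.786 × 0.214 × (1.645 + 0.842)² / 0.17² ≈ 72 per group, as stated.
- Syrinx regression: 89.1% in both arms, margin 0.135, 68 per group. SE = √(2 × 0.891 × 0.109 / 68) = 0.0534. Power = Φ(0.135/0.0534 − 1.645) = 81%, as stated.

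These two margins reproduce. No margin, sample size or power is given for revision or for spinal deformity.

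**2. Inputs for the illustration.**
- Registry revision rates: PFDD 5.0%, PFD 12.3% (Protocol 7.2.1).
- Meta-analysis revision rates: PFDD 2.1%, PFD 12.6%, p = 0.01 (Protocol 2.2, Table 2). The column headings are broken in the text. I read the last two columns as PFDD then PFD, the order that fits the other pairs.
- 72 per group (SAP 7.2), clustering ignored.
- One-sided 95% limit. SAP 7.5 does not state the level; I take it from the one-sided alpha of 0.05 in SAP 7.2.

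**3. Upper limit if the trial observed exactly these rates.** Upper limit = (PFD − PFDD) + 1.645 × SE.
- Registry: SE = √[(0.05 × 0.95 + 0.123 × 0.877)/72] = 0.0465. Limit = 0.073 + 1.645 × 0.0465 = 0.149.
- Meta-analysis: SE = √[(0.021 × 0.979 + 0.126 × 0.874)/72] = 0.0426. Limit = 0.105 + 1.645 × 0.0426 = 0.175.

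**4. Chance of declaring non-inferiority with each borrowed margin M**, if these were the true rates: Φ((M − difference)/SE − 1.645), with exact binomial enumeration in brackets.

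| Rates (PFDD vs PFD) | Upper limit | M = 0.135 | M = 0.17 |
|---|---|---|---|
| 5.0% vs 12.3% | 14.9 points: fails 0.135, meets 0.17 | 38% (39%) | 67% (68%) |
| 2.1% vs 12.6% | 17.5 points: fails both | 17% (20%) | 45% (48%) |

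**5. Clustering.** With the SAP's design effect of 1.06, 72 becomes 72/1.06 ≈ 68 per group. The registry limit is then 15.2 points and the meta-analysis limit 17.7. Neither changes sides.

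**The case against.** The strongest reply is that the sentence is a drafting carry-over. It repeats the closing sentence of the paragraph before it. The Aim 2 expectation restated in SAP 7.5 omits revision, and SAP 1.2 makes clinical symptoms and syrinx regression the main variables for this aim. On that view nobody intends a formal test of revision. This may well be right, but it is a reason to remove the sentence. As the SAP stands, the exploratory label sits beside a stated non-inferiority expectation and a stated margin comparison, and it cancels neither.

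A second reply is that each margin is tied by name to its own outcome, so a literal reader would apply neither to revision and no false verdict would follow. That is correct, and it confirms that the rule cannot be executed.

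A third concerns the illustration, and it stands. The registry table covers 2002 to 2014 and states neither a 12-month limit for repeat decompression nor a restriction to 3–9 mm syrinxes. A footnote says one patient had three repeats, so 5.0% may count procedures; removing two of the 26 would give 24/516 = 4.7%. The pass at 0.17 also depends on using the registry rather than Table 2.

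A fourth is that a margin could be specified and justified instead. In principle it could. However, the SAP is dated July 2021 and enrolment was proposed to end on December 31, 2018, so it would be hard to show that a margin added at this stage was independent of the data.

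**Conclusion.** The point holds as a secondary one. SAP 7.5 states a decision rule for second surgeries that has no threshold, and for the type of second surgery it has no direction. At the registry rates, the choice between the plan's two existing margins alone reverses the conclusion (limit 14.9 points, between 0.135 and 0.17). At the Table 2 rates, both margins would be failed. These figures are illustrations. They assume 72 per group, a one-sided 95% level, no clustering, and prior rates that do not match the trial's 12-month endpoint and population.

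Two stronger readings are not supported. A reader might infer that the sponsor means to choose a margin after seeing the data; neither document says so, and the SAP's date shows only that a margin added now would probably come late. A reader might also infer that a revision rate about two and a half times higher (12.3/5.0) would be reported as non-inferior; that requires applying 0.17 against the SAP's own wording, and it depends on the data source. The primary endpoint and the two main Aim 2 outcomes, each with its own margin, are unaffected.

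**What to change.** - In SAP 7.5, delete the margin comparison for second Chiari surgeries.
- Report the PFD minus PFDD difference in the proportion needing revision, with a cluster-adjusted two-sided 95% confidence interval, as an exploratory estimate and without a non-inferiority claim.
- Describe the type of second surgery by arm, without a test.
- Align the sentence that expects non-inferiority on revision and spinal deformity, which also has no margin. It stands in SAP 1.2 and in the Protocol under Objectives, 1.2, 3 and 9.1. Changing only the SAP would create a new conflict between the documents.

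The cost is a small wording change in both documents and the loss of any non-inferiority claim on outcomes that SAP 1.2 already calls exploratory. No new data are needed, and no properly specified test is lost.
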